# 6.1.6 Day 56 (Exit Visit)

The subject will return to the site on Day 56 ( $\pm$ 3 days) for the study exit visit and the following procedures will be performed (at the timepoints indicated in Table 1):

- Record any AEs/TEAEs and changes in concomitant medication or concomitant procedures.
- Physical Examination.
- Urine pregnancy test (for women of childbearing potential only).
- Vital sign measurement (blood pressure, pulse rate, oral body temperature).
- CTA.
- Application of study drug.
- Standardized photography of treatment area.
- CEA.
- Dermal Tolerability Assessment (investigator and subject).
- Items from Satisfaction Assessment for Rosacea Facial Redness.
- FACE-Q Satisfaction with Skin Scale.

Allergan		06 Feb 2018
CMO-MA-MED-0530	Version 2	Page 29 of 59

# 6.1.7 Early Withdrawal (or Discontinuation) Visit

If a subject's participation in the study is prematurely terminated for any reason or if the subject fails to return for a scheduled visit, every effort should be made to determine the reason. This information will be recorded in the subject's eCRF.

Upon withdrawal from the study, at any time after the first dose of study drug has taken place, all efforts should be made to invite the subject to return to the site for an early withdrawal visit and complete the exit visit procedures (Section 6.1.6). If for any reason the subject does not agree to return to the site for the exit visit, the reason and/or efforts made will be recorded.

If the subject withdraws from the study and withdraws consent for disclosure of future information, no further evaluations should be performed, and no additional data should be collected. The Sponsor may retain and continue to use any data collected before such withdrawal of consent.

### 6.2 Duration of Study

The duration of the entire study for each subject is 10 weeks. This includes a screening period of up to 2 weeks, a treatment period of 8 weeks, comprising of daily dosing of study drug and 2 energy-based therapy sessions, followed by a final exit visit at Week 8 (Day 56).

### 6.3 Acceptable Time Window Deviations

Allowed time window deviations are (assessments at screening are not described here):

**Predose** – all predose assessments on Day 1 and Day 29 should occur within 90 minutes prior to energy-based treatment. All predose assessments on Day 3, Day 31, and Day 56 should occur within 90 minutes prior to study drug administration.

**Post dose** – all assessments performed at the 1 hour, 3 hour, and 6 hour post dose timepoints should be performed within 15 minutes (ie, 1 h  $\pm$ 15min, 3 h  $\pm$ 15min, 6 h  $\pm$ 15min).

# 7 EFFICACY AND SAFETY ASSESSMENTS

#### 7.1 Efficacy and Safety and Other Measurements Assessed

The planned schedule of all study assessments is listed in Table 1.

### 7.1.1 Efficacy Assessments

The measures of efficacy are:

- Investigator's assessment of the subject's overall severity of persistent erythema associated with rosacea in the treatment area as measured by a 5-point CEA scale with photonumeric guide (Section 7.1.1.1).
- Patient's self-assessment of satisfaction using patient-reported outcomes (PROs):
  - Items from Subject Satisfaction Assessment for Rosacea Facial Redness (Section 7.1.1.2)
  - FACE-Q Satisfaction with Skin Scale (Section 7.1.1.3).
- Standardized photography of treatment area (Section 7.1.1.4).

# 7.1.1.1 Clinician Erythema Assessment

The CEA scale is the following:

Clinician Erythema Assessment (CEA) Scale				
Grade	Descriptions			
0	Clear skin with no signs of erythema a			
1	1 Almost clear of erythema, slight redness			
2	Mild erythema, definite redness			
3	3 Moderate erythema, marked redness			
4	Severe erythema, fiery redness			

a Normal healthy skin color as seen in individuals without rosacea

The CEA photonumeric guide is provided in Appendix 14.1. Prior to screening subjects, investigators will be trained in grading erythema severity using the CEA with photonumeric guide. The investigator should report the grade that best describes the average overall severity of persistent facial erythema associated with rosacea. All CEA and subject satisfaction assessments should be performed under consistent lighting conditions. The investigator may refer to the baseline (predose Day 1) facial photographs at each post-treatment timepoint to aid their assessment. The investigator must not discuss the results of the CEA with the subject, nor compare the results of assessments with previous assessments (other than the Day 1 predose assessment).

# 7.1.1.2 Items From Subject Satisfaction Assessment for Rosacea Facial Redness

The Subject Satisfaction Assessment for Rosacea Facial Redness, a PRO measure, was developed in accordance with the FDA PRO Guidance. Two questions from this assessment will be answered by subjects in the study at the timepoints listed in Table 1. These 2 questions are contained in the Items From Subject Satisfaction Assessment for Rosacea Facial Redness (Appendix 14.2). The subject will be allowed to view their baseline (predose Day 1) facial photographs during each assessment to aid their assessment.

# 7.1.1.3 FACE-Q Satisfaction With Skin Scale

The FACE-Q Satisfaction with Skin Scale (Appendix 14.3) is another PRO measure. The questionnaire should be completed by the subjects at the timepoints listed in Table 1. The subject will be allowed to view their baseline (predose Day 1) facial photographs during each assessment to aid their assessment.

# 7.1.1.4 Standardized Photography

Standardized photographs will be taken of the treatment area by trained study staff. Three photographs will be taken for each subject's face (right oblique, left oblique and frontal view) at the timepoints indicated in Table 1. Full details of the photography procedures are described in the Study Manual. Digital Image Analysis of the facial photographs for redness will be performed by a central laboratory (Canfield Scientific Inc.). The baseline (predose Day 1) photographs obtained can be used by the investigator and subject during post-treatment CEA

Allergan	06 Feb 201	
CMO-MA-MED-0530	Version 2	Page 31 of 59

and PRO assessments (Items from Subject Satisfaction Assessment for Rosacea Facial Redness and FACE-Q Satisfaction with Skin Scale) to allow comparison with the current condition of the treatment area.

# 7.1.2 Safety Assessments

The following safety measures will be collected:

- AEs and TEAEs (Section 7.1.2.1)
- Urine pregnancy tests (for women of childbearing potential only, Section 7.1.2.2)
- Vital sign measurements (blood pressure, pulse rate, and oral body temperature) (Section 7.1.2.3)
- Physical examination (Section 7.1.2.4)
- CTA (Section 7.1.2.5)
- Dermal Tolerability Assessment (Section 7.1.2.6)

## 7.1.2.1 Adverse Events

# **Adverse Event Definition**

An AE is defined as any untoward medical occurrence in a clinical study subject administered a medicinal product that does not necessarily have a causal relationship with this treatment. An AE can therefore be any unfavorable and unintended sign (including an abnormal laboratory finding), symptom, or disease temporally associated with the use of a medicinal (investigational) product, whether or not it is related to the medicinal (investigational) product. This includes an exacerbation of pre-existing conditions or events, intercurrent illnesses, drug interaction or the significant worsening of the indication under investigation that is not recorded elsewhere in the eCRF under specific efficacy assessments. Anticipated fluctuations of pre-existing conditions, including the disease under study, that do not represent a clinically significant exacerbation or worsening need not be considered AEs.

Adverse event collection will commence from the time the subject signs the ICF. It is the responsibility of the investigator to document all AEs that occur during the study. AEs will be elicited by asking the subject a nonleading question, for example, "Have you experienced any new or changed symptoms since we last asked/since your last visit?" Adverse events should be reported on the appropriate page of the eCRF.

A TEAE is any event not present prior to the initiation of the study treatments or any event already present that worsens in either intensity of frequency following exposure to the study treatments. Any AEs reported after signing the ICF and prior to study treatment are considered pretreatment AEs (PTAEs).

#### Assessment of Severity

Each AE will be assigned a category by the investigator as follows:

Mild: An AE that is easily tolerated by the subject, causes minimal discomfort, and does not interfere with everyday activities.

Allergan		06 Feb 2018
CMO-MA-MED-0530	Version 2	Page 32 of 59

Moderate:	An AE that is sufficiently discomforting to interfere with normal everyday activities; intervention may be needed.
Severe:	An AE that prevents normal everyday activities; treatment or other intervention usually needed.

If there is a change in severity of an AE, it must be recorded as a separate event.

### Assessment of Causality

Every effort will be made by the investigator to assess the relationship of the AE, if any, to the study drug. Causality should be assessed using the categories presented in the following table:

Unrelated:	Clinical event with an incompatible time relationship to study drug administration, and that could be explained by underlying disease or other drugs or chemicals or is incontrovertibly not related to the study drug.
Unlikely:	Clinical event whose time relationship to study drug administration makes a causal connection improbable, but that could plausibly be explained by underlying disease or other drugs or chemicals.
Possible:	Clinical event with a reasonable time relationship to study drug administration, but that could also be explained by concurrent disease or other drugs or chemicals.
Probable:	Clinical event with a reasonable time relationship to study drug administration, and is unlikely to be attributed to concurrent disease or other drugs or chemicals.
Very Likely/Certain:	Clinical event with plausible time relationship to study drug administration, and that cannot be explained by concurrent disease or other drugs or chemicals.

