# 5.6 Investigational Products and Therapies

# 5.6.1 Investigational Products Administered

Oxymetazoline HCl cream 1.0% will be applied in a thin layer topically to the entire face including forehead, nose, each cheek, and chin, once daily. Subjects will be instructed to apply study drug to their clean, dry face in the morning, at approximately the same time each day, starting on Day 3 through Day 56. There will be a 3 day washout period from the study drug beginning 24 hours prior to the second energy-based therapy session on Day 29 (subjects will not apply the study drug on Day 28, Day 29, and Day 30) to ensure that energy-based therapy and treatment with oxymetazoline are clearly separated in the case of any treatment-related adverse events. The Investigator should assess if any adverse events resulting from treatment with the energy-based device (eg, treatment site skin irritation or wounding) would present a risk for treatment with oxymetazoline and either delay or discontinue treatment.

For study visits, subjects will be instructed to apply the study drug at the study site. The dose will be applied after predose study assessments and procedures are completed. Site personnel

Allergan		06 Feb 2018
CMO-MA-MED-0530	Version 2	Page 22 of 59

will observe subject dosing in the clinic to ensure proper study drug application technique and retrain if necessary. Detailed instructions on study drug application will be provided to subjects (see Section 5.6.12).

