#### Documentation and Reporting of Adverse Events

Adverse events should be reported and documented in accordance with the procedures outlined below. All AEs occurring during the study must be documented on the relevant eCRF pages. The following data should be documented for each AE:

- Description of the symptom event
- Classification of 'serious' or 'not serious'
- Severity
- Date of first occurrence and date of resolution (if applicable)
- Action taken
- Causal relationship
- Outcome of event (unknown, recovered, not yet recovered, recovered with sequelae, death [with date and cause reported])

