6.2 Adverse Events

Adverse events will be coded using MedDRA version 20.1 or later to give a PT and a SOC term for each event.

An adverse event (AE) is defined as any untoward medical occurrence in a clinical investigational patient administered a pharmaceutical (investigational) product and which does not necessarily have to have a causal relationship with this treatment.

All AEs will be included in by-subject AE listings. A separate listing will be created with all the distinct levels of SOC and PT, and the verbatim investigator description reported in the study. Sorting will be by earliest observed SOC, PT within SOC and then verbatim description.

A treatment-emergent adverse event (TEAE) is a post-baseline AE where (i) there is no pretreatment AE of the same MedDRA primary SOC and PT; or (ii) the maximum severity during the post-baseline period is greater than the maximal severity of any pre-treatment AE of the same MedDRA primary SOC and PT during the screening/baseline period. Note that the post-baseline period of the study starts upon the initiation of the energy-based therapy at Day 1.

Any AEs reported after signing of the Informed Consent Form and prior to the energy-based therapy on Day 1 are considered pretreatment AEs (PTAEs)

Relationship to study drug is categorized as 'related', 'possibly related', 'unlikely related', 'not related', and 'not assessable'. Relationship to trial medication as per investigator is not expected to be missing after data cleaning. However, if relationship is confirmed as missing, the AE will be considered as treatment related as per PI.

An overall summary of frequency count and the binomial incidence proportion with associated 95% CIs will be presented to describe the incidents of TEAEs. Note that 95% CIs of the binomial incidence proportion will be presented for the overall summary analyses of TEAEs, but not for the by-visit/timepoint analyses. Percentages and corresponding 95% CIs will be displayed to 1 decimal place.

Each type of AE will be tabulated by SOC and PT within SOC. The SOC and PT within SOC will be sorted by descending frequency. If a subject has multiple occurrences (start and stop) of an event associated with a specific SOC and PT, a patient will only be counted once in the incidence count for the SOC level and once at each PT within the SOC level.

The incidence of all TEAEs by SOC and PT will be presented for the following categories:

• Any TEAE

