• Any TEAE related to energy-based therapy and leading to discontinuation of study medication

• Any TEAE related to treatment (i.e., study medication or energy-based therapy or both)

- Any TEAE by maximum severity
- Any PTAE

The following listings will be provided:

- Listing of all TEAE
- Listing of patients with TEAEs related to energy-based therapy and leading to discontinuation of study medication
- Listing of patients with TEAEs leading to discontinuation of treatment

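### Causality is rated against the study drug only, yet the SAP needs outputs on events related to energy-based therapy, and no device-causality question, scale or cut-off is specified

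*Protocol*

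**What the plan says.** Protocol 7.1.2.1 (Assessment of Causality) sets the task: "Every effort will be made by the investigator to assess the relationship of the AE, if any, to the study drug". All five categories (Unrelated, Unlikely, Possible, Probable, Very Likely/Certain) are worded on timing relative to the drug. The competing causes they name are disease and other drugs or chemicals. Possible, for instance, covers an event with a reasonable time relationship "but that could also be explained by concurrent disease or other drugs or chemicals". Unrelated has a wider last limb: "or is incontrovertibly not related to the study drug".

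The SAP's scale has the same target and different levels: "Relationship to study drug is categorized as 'related', 'possibly related', 'unlikely related', 'not related', and 'not assessable". A relationship confirmed as missing is counted as treatment related, although SAP 6.2 expects none after data cleaning.

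The SAP's outputs go further than the scale. SAP 6.2 tabulates "Any TEAE related to energy-based therapy and leading to discontinuation of study medication" and lists the patients concerned. It also tabulates "Any TEAE related to treatment (i.e., study medication or energy-based therapy or both"). SAP 6.3 asks for the same two categories for SAEs, with a listing for the first.

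Protocol 5.6.1 gives separate attribution as the reason for the washout around the second session: "to ensure that energy-based therapy and treatment with oxymetazoline are clearly separated in the case of any treatment-related adverse events".

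**The concern.** The study tests a cream added to a procedure that has skin effects of its own. Protocol 4.5 names transient purpura and post-treatment erythema. The primary objective is the safety of the combination, so a reader will want to know which component an event belongs to.

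The design spaces the two treatments in time for that purpose, and the SAP promises results that depend on device attribution. The step between them, a recorded judgement on whether the device caused the event, is not specified. At stake are the pooled related incidence, the narrower device-related outputs, and any comparison with the 8.2% drug-related rate in Protocol 8.2.

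**Working it through.** The point rests on comparing text, so the provisions are set side by side first.

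**1. What each output needs and what is defined for it**

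| SAP 6.2 / 6.3 output | Rating needed | Rating defined |
|---|---|---|
| Device-related and leading to drug discontinuation | Device | None |
| Related to drug, device or both | Drug and device | Drug only |
| Any TEAE / any SAE | None | Not needed |

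SAP section 1 lets the SAP override the protocol where they differ. That does not help here, because the SAP's own scale is also drug-only.

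**2. The protocol categories applied literally**

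- *Device event on Day 1 or 2.* The TEAE period opens with the Day 1 session (SAP 6.2) and cream starts on Day 3 (Protocol 5.3). The event fits Unrelated through its last limb, which is the right answer to the drug question. With no device rating, nothing brings the event into the pooled related category.
- *Device irritation on Day 31, after cream restarts two days after the second session.* Timing is reasonable for the drug, so Unlikely does not fit. With no disease or other drug to blame, Possible does not fit. The wording leads to Probable or higher for the drug, because the device is not an allowed alternative.
- *Rating confirmed as missing.* The event is counted as related.

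**3. The two scales**

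| Protocol level | SAP level |
|---|---|
| Unrelated | not related |
| Unlikely | unlikely related |
| Possible | possibly related |
| Probable | no stated counterpart |
| Very Likely/Certain | related (presumed) |
| no counterpart | not assessable |

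The pairing is mine, since neither document gives one. Neither says which levels count as related.

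**4. The plan's own figure that uses causality**

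Protocol 8.2 has p0 = 0.082, margin 0.14, 5% error and 80% power. With null variance at 0.082 + 0.14 = 0.222 and alternative variance at 0.082:

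n = [(1.645 × √(0.222 × 0.778) + 0.842 × √(0.082 × 0.918)) / 0.14]² = 42.67, rounded up to 43, as stated.

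This point does not alter N. It does show that the 8.2% is a drug-related rate, while the SAP's related category pools drug and device. If a share q of subjects without a drug-related event had a device-caused one (an assumption), the pooled rate would be 0.082 + 0.918q: 10.0% at q = 2%, 12.8% at 5% and 17.4% at 10%.

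**5. Direction of error (assumed counts)**

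Suppose that of 45 subjects, 4 have a drug-caused event and 3 others a device-caused event only. The true drug-related rate is 4/45 = 8.9% and the true pooled rate is 7/45 = 15.6%.

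- All three device events before the first cream, rated Unrelated: pooled reads 4/45 = 8.9%, which is 3/45 = 6.7 points too low.
- All three after dosing and attributed to the drug: pooled reads 15.6%, which is correct, but the drug-related rate also reads 15.6%, which is 6.7 points too high.

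**The case against.** The strongest reply is that the eCRF is not among the documents and may already hold a device-causality field. Protocol 7.1.2.1 (Documentation and Reporting) requires only "Causal relationship" for each AE, without saying to what. Protocol 5.6.1 expects the investigator to consider events resulting from the device, and the action-taken options include stopping or interrupting energy-based therapy. The SAP's planned outputs are consistent with such a field. This stands as far as it goes: whether the data exist cannot be settled from the documents. An action taken is not a causality rating, however, and a field with no defined question, scale or cut would still be applied differently across the four sites.

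A reader might infer more than the text supports:

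- *That the device outputs cannot be filled or must show zero.* That is a claim about the eCRF. The drug part of the pooled category can be filled from the defined scale.
- *That device harms have no valid category.* A Day 1 device event fits Unrelated. What is missing is a category that records a positive link to the device.
- *That the SAP plans general device-harm tables.* Its only device-specific outputs also require discontinuation of the cream.
- *That the bias runs one way.* The working shows both directions, and the rule for missing ratings pushes towards related.

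No primary endpoint uses causality. New device events count in Any TEAE, all AEs are listed, and onset dates allow some attribution of Day 1 and Day 2 events by timing.

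**Conclusion.** The concern holds in this form: both documents specify causality against study drug only, the protocol's categories omit the device as an alternative cause, and SAP 6.2 and 6.3 need device relatedness that neither document defines. The scales are also unaligned, with no stated cut for related.

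Followed as written, pre-cream device events fall out of the pooled related category and later ones may be charged to the drug. The size depends on how many device-only events occur and when. The 6.7-point figure rests on assumed counts and a literal reading of the categories. Investigators using judgement could do better, but the plan does not tell them how.

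The primary TEAE and SAE incidences, dermal tolerability and telangiectasia results are not affected. The plan should be corrected, but the gap does not undermine the study's main result.

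**What to change.** 1. In Protocol 7.1.2.1, require two causality ratings for every AE and SAE, one to study drug and one to energy-based therapy, on one scale.
2. Name energy-based therapy among the alternative explanations in the study-drug categories.
3. Confirm that the eCRF holds both fields, or add the missing one.
4. In SAP 6.2 and 6.3, use the same scale and prespecify which levels count as related (for example, Possible or higher).
5. Derive the device-related and combined categories from the two fields.

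The cost is text edits in both documents and at most one added eCRF field, with no added visit or procedure. Investigators spend slightly more time per AE, and the reported treatment-related rate may rise.

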### **Action Taken**

The investigator will describe the action taken in the appropriate section of the eCRF, as follows:

- Study drug stopped
- Study drug temporarily interrupted
- Energy-based therapy stopped
- Energy-based therapy temporarily interrupted
- Concomitant medication

